9.3.2 Exclusion Criteria

Subjects who meet any of the following criteria will be excluded from this study:

1. Females who are breastfeeding or pregnant at Screening or Baseline (as documented by a positive beta-human chorionic gonadotropin test. A separate baseline assessment is required if a negative screening pregnancy test was obtained more than 72 hours before the first dose of study drug. Females of child-bearing potential who:
 - within 28 days before study entry, did not use a highly effective method of contraception, which includes any of the following:
 - total abstinence (if it is their preferred and usual lifestyle)
 - an intrauterine device or intrauterine hormone-releasing system
 - an oral contraceptive (Subject must be on a stable dose of the same oral contraceptive product for at least 28 days before dosing and throughout the study and for 28 days after study drug discontinuation.)
 - have a vasectomized partner with confirmed azoospermia
 - do not agree to use a highly effective method of contraception (as described above) throughout the entire study period and for 28 days after study drug discontinuation.

For sites outside of the European Union, it is permissible that if a highly effective method of contraception is not appropriate or acceptable to the subject, then the subject must agree to use a medically acceptable method of contraception, ie, double-barrier methods of contraception such as condom plus diaphragm or cervical/vault cap with spermicide.

NOTE: All females will be considered to be of child-bearing potential unless they are postmenopausal (amenorrhic for at least 12 consecutive months, in the appropriate age group, and without other known or suspected cause) or have been sterilized surgically (ie, bilateral tubal ligation, total hysterectomy, or bilateral oophorectomy, all with surgery at least 1 month before dosing)

2. Any condition that may be contributing to cognitive impairment above and beyond that caused by the subject's AD
3. Subjects with a history of seizures within 5 years of Screening or subjects with disturbance likely to be due to seizures within 5 years of Screening
4. History of transient ischemic attacks (TIA) or stroke within 12 months of Screening
5. Modified Hachinski Ischemia Score greater than 4 at Screening
6. Any of the following psychiatric symptoms:

- Psychiatric diagnosis or symptoms, (eg, hallucinations, major depression, or delusions) that, in the opinion of the investigator, could interfere with study procedures
 - Has a “yes” answer to C-SSRS suicidal ideation items 4 or 5, or any suicidal behavior within 6 months before Screening, at Screening, or at the Randomization Visit, or has been hospitalized or treated for suicidal behavior in the past 5 years before Screening
7. Have any contraindications to MRI scanning, including cardiac pacemaker/defibrillator, ferromagnetic metal implants (eg, in skull and cardiac devices other than those approved as safe for use in MRI scanners) or
- Have any evidence of other clinically significant lesions that could indicate a dementia diagnosis other than AD on brain MRI at Screening.
 - Exhibit other significant pathological findings on central read of the brain MRI at Screening, including but not limited to: an area of superficial siderosis; evidence of cerebral vasogenic edema; evidence of cerebral contusion, encephalomalacia, aneurysms, vascular malformations, or infective lesions; evidence of multiple lacunar infarcts; evidence of stroke involving a major vascular territory; severe small vessel or diffuse white matter disease as defined by a score of 3 on the age-related white matter changes score (Wahlund, et al., 2001); space occupying lesions; or brain tumors (however, lesions diagnosed as meningiomas or arachnoid cysts and less than 1 cm at their greatest diameter need not be exclusionary). (revised per Amendment 03)
8. Subjects who have a history of moderate to severe hepatic impairment (eg, Child-Pugh Class B or C). Any 2 of the following criteria at Screening would exclude the subject: INR \geq 1.7; bilirubin \geq 1.5 \times ULN; albumin < LLN; ascites or hepatic encephalopathy. Please note that a single significant abnormality could meet criteria for moderate impairment. (revised per Amendment 01)
9. Results of laboratory tests conducted during screening that are outside the following limits:
- Absolute lymphocyte count (ALC) below Lower Limit of Normal (LLN) or below 800 per mm³ (whichever is higher); ALC will be derived from the complete blood count (CBC) with differential representing the normal lymphocytes (with atypical lymphocytes removed and presented as a separate count if they are present) and calculated by the white blood cell count \times percentage of lymphocytes. (revised per Amendment 01)
 - Thyroid stimulating hormone (TSH) above normal range. Other tests of thyroid function with results outside the normal range should only be exclusionary if they are considered clinically significant by the investigator (this applies to all subjects whether or not they are taking thyroid supplements)

- Abnormally low (below LLN) serum Vitamin B12 levels (if subject is taking Vitamin B12 injections, level should be at or above the LLN)

10. Subjects at risk of increased risk of infection, specifically:

- Subjects with chronic viral hepatitis. Subjects with a history of chronic viral hepatitis C may be included if they meet the following requirements:
 - 1) evidence of treatment with direct antiviral combination therapy
 - 2) evidence of sustained virological response at least 12 weeks post-treatment

The inclusion of subjects with a history of chronic viral hepatitis C must be discussed and agreed with the Medical Monitor. (revised per Amendment 03)

- A history of active tuberculosis disease (TB), a history of ophthalmic shingles or a history of ocular herpes simplex virus (HSV) infection (revised per Amendment 03)
- Any active infection within the last 4 weeks before randomization. For such cases, the timing of randomization can be extended (up to 4 weeks) to allow the infection to resolve
- Any immunological disease which is not adequately controlled, or which requires treatment with biologic drugs during the study. History of immunoglobulin deficiency or other immunodeficiency disorders (including subjects known to be HIV positive)

11. Have received any live/live attenuated vaccine in the 3 months before randomization

12. Any chronic inflammatory disease that is not adequately controlled or that requires systemic immunosuppressive or immunomodulatory therapy. (revised per Amendment 03)

NOTE: The following subjects do not need to be excluded:

- Subjects with seasonal or perennial allergic rhinitis, asthma, or chronic obstructive pulmonary disease where the condition is considered to be stable and adequately controlled by inhaled steroids.
- Hashimoto's thyroiditis but who are stable on thyroid replacement therapy and not on systemic immunosuppressive therapy.
- Cutaneous manifestations of immunological disease that do not require systemic immunosuppressive therapy or systemic immunomodulatory therapy (ie, topical steroid treatment is permitted)

13. Any other clinically significant abnormalities, such as:

- Physical examination or vital signs at Screening or Baseline that in the opinion of the investigator require further investigation or treatment or may interfere with study procedures or safety. (revised per Amendment 03)
 - Laboratory tests or ECG at Screening that in the opinion of the investigator require further investigation or treatment or may interfere with study procedures or safety. (revised per Amendment 03)
 - Other medical conditions (eg, cardiac, respiratory, gastrointestinal, psychiatric, renal disease) which are not adequately and stably controlled, or which in the opinion of the investigator(s) could affect the subject's safety or interfere with the study assessments (revised per Amendment 01)
 - Illiteracy, or severe visual or hearing impairment that would prevent the subject from performing psychometric tests accurately
14. A prolonged QTc interval calculated using Fridericia's formula (QTcF) interval (QTcF greater than 450 ms according to central reading at Screening). (revised per Amendment 03) If the QTcF is greater than 450 ms on the first single 12-lead ECG, 2 additional 12-lead ECGs will be performed 1 minute apart and the mean of the 3 QTcF values will be calculated.
15. Malignant neoplasms within 5 years of Screening (except for basal or squamous cell carcinoma in situ of the skin, or localized prostate cancer in male subjects with treatment cycles completed at least 6 months prior to screening). Subjects who had malignant neoplasms but who have had at least 5 years of documented uninterrupted remission before Screening need not be excluded.
16. Hypopigmentation conditions (eg, albinism and vitiligo). Hypopigmentation associated with scarring need not be exclusionary
17. Known or suspected history of drug or alcohol abuse or dependence within 2 years before Screening
18. Taking prohibited medications
19. Have participated in a clinical study involving:
- any therapeutic monoclonal antibody, protein derived from a monoclonal antibody, immunoglobulin therapy, or vaccine within 6 months before Screening for whom it cannot be documented that they were randomized only to placebo or never received study drug
 - elenbecestat (E2609)
 - any new chemical entity for AD with last study drug dose occurring within 6 months prior to Screening unless it can be documented that the subject received only placebo

- any other investigational medication (unless it can be documented that the subject received only placebo) or device within 8 weeks or 5 half-lives (whichever is longer) before randomization

20. Planned surgery which requires general, spinal or epidural anesthesia that would take place during the study. Planned surgery which requires only local anesthesia and which can be undertaken as day case without inpatient stay postoperatively need not result in exclusion if in the opinion of the investigator this operation does not interfere with study procedures and subject safety.

9.3.3 Removal of Subjects from Therapy or Assessment

The investigator may withdraw the subject from the study at any time for safety or administrative reasons. The subject may stop study drug or withdraw from the study at any time for any reason.

Absolute lymphocyte count from the hematology and differential panel will be monitored during the study. ALC will be derived from the CBC with differential representing the normal lymphocytes (with atypical lymphocytes removed and presented as a separate count if they are present) and calculated by the white blood cell count \times percentage of lymphocytes. (revised per Amendment 01) Should a subject develop a Grade 2 or greater lymphocytopenia (less than $800/\text{mm}^3$), the absolute lymphocyte count test should be repeated as soon as possible with the repeat blood sample drawn no later than 5 calendar days from the date of the original test. (revised per Amendment 03) If confirmed, study drug administration should be interrupted for a minimum period of 2 weeks and for a maximum period of 4 weeks. Restart of study drug may take place only when absolute lymphocyte count returns to greater than LLN. Absolute lymphocyte count will be measured 4 weeks after restart of study drug. Subsequent measurements of absolute lymphocyte counts will follow the schedule of assessments (Table 4) and any results showing a Grade 2 or greater lymphocytopenia (less than $800/\text{mm}^3$) should be handled as above. If a 2nd occurrence of Grade 2 or greater lymphocytopenia (less than $800/\text{mm}^3$), that is confirmed on repeat testing, occurs within 6 months, then the subject should be discontinued permanently from the study drug.

Subjects who develop moderate or severe hepatic impairment (eg, Child-Pugh Class B or C) during the study must discontinue study drug. (revised per Amendments 01 and 02) Moderate or severe hepatic impairment are defined as any 2 of the following criteria: $\text{INR} \geq 1.7$; bilirubin $\geq 1.5 \times \text{ULN}$; albumin $< \text{LLN}$; ascites or hepatic encephalopathy. Please note that a single significant abnormality could meet criteria for moderate impairment. (revised per Amendment 02)

Subjects who develop seizures will be discontinued from study drug. (revised per Amendment 02)

In the event that a subject develops a severe infection, study drug administration should be interrupted for a maximum period of 4 weeks. Examples of severe infections include the following: sepsis; deep tissue (invasive) infection; any infection requiring IV antibiotics; any

infection requiring hospitalization (if outpatient at onset); any infection leading to need for oxygen, pressors or fluids to support blood pressure, or intubation; any infection that requires major surgical intervention; pseudomembranous colitis due to *C. difficile*; typhlitis; osteomyelitis; and meningitis. Subjects who recover from severe infections within 4 weeks may resume treatment if deemed appropriate by the investigator after consultation with the Medical Monitor. Subjects should permanently discontinue study drug if the severe infection has not resolved within 4 weeks. (revised per Amendment 02)

As described under Dermatologic Assessment in Section 9.5.1.5.5, in the event that a subject develops any skin rash of moderate to severe intensity, or any rash lasting more than 72 hours regardless of severity (with the exception of oral or genital herpes as described in the next paragraph), study drug administration should be interrupted for a maximum period of 4 weeks and a dermatologic consult will be requested regardless of whether the rash is considered drug related or due to other causes. For cases where the investigator suspects a drug rash, regardless of severity, the subject will be discontinued from study drug, a dermatologic consult will be requested, and a skin biopsy will be performed to confirm the diagnosis. The skin rash will be treated as per standard care and will be followed up until resolution regardless of etiology or severity. Subjects who recover from skin rash within 4 weeks may resume treatment if in the opinion of the dermatologic consult, the rash was not drug related and it is deemed appropriate by the investigator after consultation with the Medical Monitor. Subjects should permanently discontinue study drug if the skin rash has not resolved within 4 weeks or returns during rechallenge. (revised per Amendment 02)

In the event that a subject develops moderate to severe oral or genital herpes, study drug administration should be interrupted for a maximum period of 4 weeks. Subjects who develop a mild case of oral or genital herpes may remain on study drug even if the event lasts more than 72 hours. Subjects who recover from moderate to severe oral or genital herpes within 4 weeks may resume treatment if it is deemed appropriate by the investigator after consultation with the Medical Monitor. Subjects should permanently discontinue study drug if the oral or genital herpes has not resolved within 4 weeks or returns during rechallenge. (revised per Amendment 02)

Subjects who discontinue study drug early must complete the ED Visit (within 7 days of the last dose of study drug) and the Follow-Up Visits (1 and 3 months after the last dose of study drug). These Follow-Up Visits will be conducted to monitor efficacy and safety parameters after early withdrawal from the study or discontinuation of study drug.

All subjects who discontinue study drug before reaching 12 months of treatment will also be asked to return to the clinic for a 12-month clinical assessment and then again at 24 months. Subjects who discontinue treatment between 12 and 24 months of treatment will be asked to return to the clinic for a 24 month clinical assessment. Subjects who discontinue early from study drug are considered “on study” as long as they continue to return for their regularly scheduled clinical assessments at 12 and 24 months as outlined above, at which efficacy and quality of life will be assessed along with concomitant medications and AEs. However, subjects who discontinue study drug early are not considered to have ‘completed’ the study as a final Subject Disposition.

The primary reason for discontinuation and all other reason(s) contributing to the subject's discontinuation from study drug(s) should be collected on the ED from study drug electronic case report form (eCRF) page. In addition, the date of last dose of study drug(s) will be recorded on the Study Drug Dosing eCRF page. If a subject discontinues study treatment and the study at the same time, the end-of-study procedures (Final Visit) will be followed (see [Section 9.5.5](#)).

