9.5.4.2 Reporting of Pregnancy and Exposure to Study Drug Through Breastfeeding

Any pregnancy in which the estimated date of conception is either before the last visit or within 28 days of last study treatment, or any exposure to study drug through breastfeeding during study treatment or within 28 days of last study treatment, must be reported.

If an adverse outcome of a pregnancy is suspected to be related to study drug exposure, this should be reported regardless of the length of time that has passed since the exposure to study treatment.

A congenital anomaly, death during perinatal period, an induced abortion, or a spontaneous abortion are considered to be an SAE and should be reported in the same time frame and in the same format as all other SAEs (see Reporting of SAEs [Section 9.5.4.1]).

Pregnancies or exposure to study drug through breastfeeding must be reported by fax or email as soon as possible but no later than 1 business day from the date the investigator becomes aware of the pregnancy. The contact information for the reporting of pregnancies and exposure to study drug through breastfeeding is provided in the Investigator Study File. The Pregnancy Report Form must be used for reporting. All pregnancies must be followed to outcome. The outcome of the pregnancy must be reported as soon as possible but no later than 1 business day from the date the investigator becomes aware of the outcome.

A subject who becomes pregnant must be withdrawn from study treatment.

Pregnancies in partners of male study subjects do not need to be reported. (revised per Amendment 03)

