9.5.5 Completion/Discontinuation of Subjects

A subject may elect to withdraw from the study at any time for any reason. All subjects who discontinue study drug early for any reason will undergo an ED Visit within 7 days of their last dose of study drug (see [Section 9.1.2.2](#)). In addition, Follow-Up Visits will be scheduled 4 and 12 weeks after the last dose of study drug (Visit 14 and Visit 15, respectively) (see [Section 9.1.2.2](#)). These Follow-Up Visits will be conducted to monitor efficacy and safety parameters after early withdrawal from the study or discontinuation of study drug. See [Table 4](#) for full details of the assessments to be performed at these visits.

All subjects who discontinue study drug before reaching 12 months of treatment will also be asked to return to the clinic for a 12 month clinical assessment and then again at 24 months. Subjects who discontinued treatment between 12 and 24 months of treatment will be asked to return to the clinic for a 24 month clinical assessment. Subjects who discontinue early from study drug are considered “on study” as long as they continue to return for their clinical assessments at 12 and 24 months as outlined above, at which efficacy and quality of life will be assessed along with concomitant medications and AEs. However, subjects who discontinue study drug early are not considered to have ‘completed’ the study as a final Subject Disposition. A subject removed from the study for any reason may not be replaced.

The investigator will promptly explain to the subject involved that the study will be discontinued for that subject and provide appropriate medical treatment and other necessary measures for the subject. A subject who has ceased to return for visits will be followed up by mail, phone, or other means to gather information such as the reason for failure to return, the status of treatment compliance, the presence or absence of AEs, and clinical courses of signs and symptoms.

The primary reasons for early withdrawal from the study are: AE, lost to follow-up, subject choice, withdrawal of consent, pregnancy, study terminated by sponsor, and other. The secondary reasons for early withdrawal from the study are: AE, subject choice, and other.

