9.7.1.6.1 PRIMARY EFFICACY ANALYSIS

The primary analysis will be based on an intent to treat philosophy without regard to adherence to treatment. The primary analysis of the change from baseline in CDR-SB at 24 months will be performed to compare elenbecestat (E2609) 50 mg per day versus placebo using a linear mixed effects model for repeated measures (MMRM) on the FAS. The MMRM model will include baseline CDR-SB as a covariate, with treatment group, visit, randomization stratification variables (ie, region [7 levels], clinical dementia [yes, no], and concurrent AD medication use at randomization (Visit 2) [yes, no]), and treatment group-by-visit interaction as fixed effects. An unstructured covariance matrix will be employed to model the covariance of within subject effect; if MMRM fails to converge then a covariance structure with fewer parameters from the following list will be employed according to the prespecified order in the list until the MMRM converges. The list of covariance structure will include Heterogeneous Toeplitz, Toeplitz, Heterogeneous Compound Symmetry, and Compound Symmetry. This primary analysis will include all observed post baseline data of the change from baseline in CDR-SB without imputation of missing values. The treatment effect for elenbecestat (E2609) versus placebo will be compared at 24 months based on MMRM model. The LS means and difference in LS means between elenbecestat (E2609) treatment group and placebo, and corresponding 95% CI will be presented.

The null hypothesis is that there is no difference in the mean change from baseline in CDR-SB at 24 months between elenbecestat (E2609) 50 mg per day and placebo. The corresponding alternative hypothesis is that there is a difference in the mean change from baseline in CDR-SB at 24 months between elenbecestat (E2609) 50 mg per day and placebo.

The primary analysis will be repeated to minimize the impact of change in concomitant AD medications where efficacy data after initiation of new AD medications and increase of current AD medications will be censored.

The following sensitivity analysis will be conducted to evaluate the impact of missing data: the primary endpoint will be analyzed using ANCOVA after multiple imputation. The ANCOVA model will include baseline CDR-SB as a covariate, with treatment group and randomization stratification variables as factors.

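### Section 9.3.3 lets the investigator end study participation, not only study drug, so month-24 CDR-SB can go uncollected for reasons that may relate to treatment

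*Protocol*

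**What the plan says.** Section 9.3.3 opens with the investigator's power: "The investigator may withdraw the subject from the study at any time for safety or administrative reasons". The next sentence gives the subject two distinct options: "The subject may stop study drug or withdraw from the study at any time for any reason". So the first sentence is not loose wording for stopping drug.

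Sections 9.5.5 and 9.7.1.3 keep separate lists of reasons for leaving the study and for stopping drug. On the former: "The primary reasons for early withdrawal from the study are: AE, lost to follow-up, subject choice, withdrawal of consent, pregnancy" (the list continues).

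For subjects who stop drug, Section 9.3.3 sets up off-drug follow-up: "All subjects who discontinue study drug before reaching 12 months of treatment will also be asked to return to the clinic" for month-12 and month-24 assessments. Those who stop between months 12 and 24 are asked back at month 24. Table 4, footnote b, lists the CDR among the assessments at these visits. A simultaneous exit is handled differently: "If a subject discontinues study treatment and the study at the same time, the end-of-study procedures (Final Visit) will be followed".

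Section 9.7.1.6.1 defines the analysis: "The primary analysis will be based on an intent to treat philosophy without regard to adherence to treatment". It is an MMRM on observed CDR-SB changes with nothing imputed.

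**The concern.** An analysis that ignores adherence needs month-24 CDR-SB from subjects who are off drug. The protocol plans to collect it, but the recall starts from stopping drug, while the investigator's power reaches further and can end participation. Analysis cannot recover a score that was never collected.

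Safety exits could differ between arms. Section 7.1 reports some CD4 reduction at 50 to 100 mg, the range that includes the study dose. They could also relate to the outcome, because Section 9.5.1.5.1 makes cognitive decline that the investigator judges excessive reportable as an adverse event. The MMRM corrects for such losses only as far as earlier CDR scores predict the missing one. At stake are some bias in the estimated treatment difference and a small loss of information at month 24.

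**Working it through.** **Does the text leave a gap?**

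1. Study withdrawal by the investigator: permitted for safety or administrative reasons (9.3.3).
2. Adverse event as a reason for leaving the study: listed (9.5.5, 9.7.1.3).
3. Month-24 CDR after stopping drug: requested (9.3.3; Table 4, footnote b).
4. Month-24 CDR after withdrawal from the study: no provision. Subjects off drug count as on study only while they return for the 12- and 24-month assessments. A simultaneous exit goes to a Final Visit that appears as such in neither 9.5.5 nor Table 4.
5. CDR shortly after the last dose: Table 4 schedules it at the ED Visit and at Visits 14 and 15. Section 9.3.3 says the Follow-Up Visits also serve after early withdrawal from the study. That collection ends 12 weeks after the last dose.

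The gap is real and is confined to month 24 (and month 12 for early exits).

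**The plan's sample size (9.7.2).** Inputs: placebo change 1.75, reduction 25%, SD 2.05, power 90%, two-sided alpha 0.05, dropout 30%.

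- Effect = 0.25 × 1.75 = 0.4375.
- n per arm = 2 × (1.960 + 1.282)² × 2.05² / 0.4375² ≈ 462 (463 with the t distribution).
- Inflated for dropout: 463 / 0.70 ≈ 662 per arm, 1324 in total. The stated 665 per arm (1330) is reproduced closely.
- With 665 × 0.70 = 465.5 per arm, power is 90.2% and SE = 2.05 × √(2/465.5) = 0.134.

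**Information.** Power of the t-test at 665 per arm, by share of month-24 data lost: 25%, 92.0%; 30%, 90.2%; 32%, 89.4%; 35%, 88.0%; 40%, 85.3%. A few extra losses cost little power.

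**Bias, on assumptions not in the protocol.** Let e be the excess proportion withdrawn this way in the active arm over placebo. Let k be how much worse their unseen month-24 change is than the model predicts, taken as equal in both arms. Then bias = e × k, overstating the benefit. The percentage is of 0.4375.

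| e | k = 0.5 | k = 1.0 | k = 2.0 |
|---|---|---|---|
| 1% | 0.005 (1.1%) | 0.010 (2.3%) | 0.020 (4.6%) |
| 2% | 0.010 (2.3%) | 0.020 (4.6%) | 0.040 (9.1%) |
| 5% | 0.025 (5.7%) | 0.050 (11.4%) | 0.100 (22.9%) |

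In standard errors the range is 0.005/0.134 = 0.04 to 0.100/0.134 = 0.74.

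**The case against.** The case against has real force.

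- **The clause permits; it does not require.** The named safety rules in 9.3.3 (lymphocytopenia, hepatic impairment, seizures, severe infection, rash, herpes) interrupt or stop drug only. Section 9.5.4.2 does the same: "A subject who becomes pregnant must be withdrawn from study treatment". A reader might infer that the analysis will lose month-24 data for treatment-related reasons. The protocol supports only that it can, and administrative reasons are not in themselves tied to treatment.
- **The recall might be read to cover these subjects.** Anyone withdrawn from the study also stops drug. That reading is possible, but the separate route for simultaneous exits leaves it unsettled, so the gap stands.
- **Some data remain.** The MMRM uses CDR scores up to the exit and any from the Follow-Up Visits, so these subjects are not simply assumed to behave like those who stayed. A multiple-imputation sensitivity analysis is planned. The 30% dropout allowance protects power, though not against bias.
- **A CDR is not always possible.** A reader might infer that an adverse event or administrative problem never prevents one. Death, incapacity or loss of the study partner can. The list in 9.5.5 has no category for death, so a fatal event would naturally fall under AE.
- **The pregnancy entries do not conflict.** Section 9.5.5 gives disposition categories and 9.5.4.2 gives a rule. At ages 50 to 85 the matter is negligible.
- **Type I error.** A reader might infer inflation. Loss of benefit after stopping drug gives no bias under the null, because there is no benefit to lose. Inflation would need unequal withdrawal between arms plus extra unmodelled decline unrelated to lost benefit, and the protocol gives a figure for neither.

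**Conclusion.** The concern holds as a gap in the follow-up scheme. Section 9.3.3 permits an exit that the off-drug recall does not clearly cover, and this fits badly with a primary analysis that disregards adherence. Where the reason is safety, the missing CDR-SB may be related to treatment.

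The size is unknown, because the protocol gives no rate of investigator-initiated withdrawal. The 0.005 to 0.10 point range rests wholly on the assumed excess (1–5%) and unmodelled decline (0.5–2.0 points). The upper end is severe: 2.0 points exceeds the whole assumed placebo decline of 1.75. At the lower end the effect is trivial. The sample size needs no correction, and neither certain bias nor an inflated type I error follows from the documents. The change is worth making because it is cheap and protects the primary outcome in a trial intended as pivotal.

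**What to change.** Reword the opening of 9.3.3. When the investigator acts for safety or administrative reasons, the default is to stop study drug or the procedure concerned. The subject stays in the study and is asked to attend the Follow-Up Visits and the 12- and 24-month CDR assessments where feasible. State the exceptions:

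- consent is withdrawn, or the representative's consent or the subject's assent required by Section 5.3 is lacking;
- continued participation is ruled out, for example by death, incapacity, no available study partner, or a decision under Section 9.5.1.5.9 after a positive suicidality assessment.

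Align the simultaneous-exit sentence in 9.3.3 and the text of 9.5.5 with this, including which visit Final Visit means. Keep AE on the study-withdrawal list for fatal or incapacitating events, and keep loss to follow-up. Have the disposition form record whether a month-24 CDR was sought.

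This concerns data collection only; the rules on when study drug is stopped stay as they are. The cost is protocol wording, a minor eCRF change and a few more off-drug visits of a kind already scheduled.
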